Wear and Replacement Schedules	Wear Schedule: daily wear (DW) Replacement Schedule: approximately 2 weeks
Objectives	The primary objective of this study is to demonstrate non-inferiority of the Test lens compared to the Control lens with respect to CLUE comfort, Slit Lamp Findings and Monocular logMAR Distance Visual Acuity. This study will also aim to show the Fit Acceptance rate is at least 90% in order to assess performance of the Test lens for eventual Design Validation and/or Claims studies.
Study Endpoints	Primary Endpoints: 
• Monocular logMAR distance visual acuity• Biomicroscopy• Fit acceptance rate• Overall CLUE comfort Secondary Endpoints: 
• Overall CLUE vision• Overall CLUE handling

[figure not shown]
Study Design	
This study is a randomized, 5-visit, partial subject-masked, 2×3 bilateral crossover, dispensing trial. The study lenses will be worn as daily wear (DW) for a period of 2 weeks each with one of the study lenses being worn twice. Each study lens is expected to be worn at least five (5) days per week for at least six (6) hours per day worn. There will be no washout period between study lenses.
 
See the flow chart at the end of the synopsis table for the schematic of the study visits and procedures of main observations.

Sample Size	
Approximately 130 eligible subjects will be enrolled and randomized into the study. Approximately 120 subjects are targeted to complete the study. A replacement subject may be enrolled if a subject discontinues from the study prematurely; the decision whether to enroll replacement subjects will be made by the joint agreement of the Investigator and Sponsor.

Study Duration	
Subjects will wear the Test and control lenses for 2 weeks each in random order with one of the study lenses being worn twice for a total of 6 weeks per subject. The enrollment period will be 2 weeks, making the entire study approximately 8 weeks in duration.

Anticipated Study Population	
Approximately 130 subjects will be enrolled to ensure that at least 120 subjects will complete the study. Enrolled subjects will be habitual wearers of spherical contact lenses. All subjects will be the age of ≥ 18 and ≤ 49.

Eligibility Criteria (Inclusion Criteria)	
Potential subjects must satisfy all of the following inclusion criteria to be enrolled in the study:
 
 1. The subject must read and sign the Informed Consent form. 2. The subject must appear able and willing to adhere to the instructions set forth in this clinical protocol. 3. Healthy adult males or females age ≥ 18 and ≤ 49 years of age with signed informed consent. Eligible presbyopes will be those that wear full distance contact lenses in both eyes, then wear reading glasses over them. 4. The subject's optimal vertexed spherical equivalent distance correction must be between -1.00 and -6.00D. 5. The subject's refractive cylinder must be ≤ 1.00D in each eye. 6. The subject must have visual acuity best correctable to 20/25+3 or better for each eye. 7. Subjects must own a wearable pair of spectacles. 8. The subject is a current spherical soft contact lens wearer (defined as a minimum of 6 hours of DW per day, at least 5 days per week, for a minimum of 1 month prior to the study) and willing to wear the study lenses on a similar basis. 9. Subjects must be able and willing to wear the study lenses at least 6 hours a day, a minimum of 5 days per week 10. The subject must have normal eyes (i.e., no ocular medications or infections of any type).
Eligibility Criteria (Exclusion Criteria)	
Potential subjects who meet any of the following criteria will be excluded from participating in the study:
 
 1. Currently pregnant or lactating (subjects who become pregnant during the study will be discontinued). 2. Any systemic disease, autoimmune disease, or use of medication, which may interfere with contact lens wear. This may include, but not be limited to, diabetes, hyperthyroidism, recurrent herpes simplex/zoster, Sjögren's syndrome, xerophthalmia, acne rosacea, Stevens-Johnson syndrome, and immunosuppressive diseases or any infectious diseases (e.g. hepatitis, tuberculosis). 3. Use of any of the following medications within 1 week prior to enrollment: oral retinoid isotretinoin (e.g. Accutane), oral tetracyclines, topical scopolamine, oral

	
(e.g., Chlor-Trimeton, and Benadryl) and ophthalmic antihistamines, oral phenothiazines (e.g., Haldol, Mellaril, Thorazine, Elavil, Pamelor, Compazine), oral and ophthalmic Beta-adrenergic blockers (e.g., Propranolol, Timolol, and Practolol), systemic steroids, and any prescribed or over the counter (OTC) ocular medication.
 
 4. Entropion, ectropion, extrusions, chalazia, recurrent styes, glaucoma, history of recurrent corneal erosions, aphakia, or moderate or above corneal distortion. 5. Any previous, or planned, ocular or intraocular surgery (e.g., radial keratotomy, PRK, LASIK, etc.). 6. Any Grade 3 or greater slit lamp findings (e.g., edema, corneal neovascularization, corneal staining, tarsal abnormalities, conjunctival injection) on the FDA classification scale, any previous history or signs of a contact lens-related corneal inflammatory event (e.g., past peripheral ulcer or round peripheral scar), or any other ocular abnormality that may contraindicate contact lens wear. 7. Any known hypersensitivity or allergic reaction to Optifree®PureMoist® multi-purpose care solution or Eye-Cept® rewetting drop solution 8. Any ocular infection, allergy or clinically significant ocular disease (e.g. corneal edema, uveitis, severe keratoconjunctivitis sicca, ocular hypertension), or ocular conditions (e.g. strabismus), which might interfere with the study. 9. Any corneal distortion resulting from previous hard or rigid gas permeable contact lens wear. 10. Toric, extended wear, monovision or multi-focal contact lens correction. 11. Participation in any contact lens or lens care product clinical trial within 30 days prior to study enrollment. 12. Participation in clinical trials involving the Test lens within 3 months prior to study enrollment. 13. History of binocular vision abnormality or strabismus. 14. Employee, relative or friends of employees of any ophthalmic company, or investigational clinic (e.g., Investigator, Coordinator, Technician).
--	---

Disallowed Medications/Interventions	Use of any of the following medications within 1 week prior to enrollment: oral retinoid isotretinoin (e.g. Accutane), oral tetracyclines, topical scopolamine, oral (e.g. Seldane, Chlor-Trimeton, and Benadryl) and ophthalmic antihistamines, oral phenothiazines (e.g., Haldol, Mellaril, Thorazine, Elavil, Pamelor, Compazine), oral and ophthalmic Beta-adrenergic blockers (e.g., Propranolol, Timolol, and Practolol), systemic steroids, and any prescribed or over the counter (OTC) ocular medication
Measurements and Procedures	Monocular distance visual acuity on logMAR scale using ETDRS charts, physiological responses, fitting characteristics, individual performance metrics, CLUE comfort, vision and handling.
Microbiology or Other Laboratory Testing	The optical bench will be used to measure the light transmission characteristics for all worn test lenses. The findings are for internal information only and will not be part of the final report.
Study Termination	The occurrence of one or more Unanticipated Adverse Device Effect (UADE), or any SAE where relationship to study agent cannot be ruled out, will result in stopping further dispensing investigational product. In the event of a UADE or SAE, the Sponsor Medical Monitor may unmask the control lens of subject(s) and may discuss this with the Principal Investigator before any further subjects are enrolled.
Ancillary Supplies/ Study-Specific Materials	Opti-Free® PureMoist®, Preservative free rewetting drops/artificial tears
Principal Investigator(s) and Study Institution(s)/Site(s)	A full list of Principal Investigators, clinical sites, and institutions is kept separately from the Study Protocol and is included in the study Trial Master File.

Figure 1: Study Flowchart

COMMONLY USED ABBREVIATIONS AND DEFINITIONS OF TERMS

ADD	Plus Power Required For Near Use
ADE	Adverse Device Effect
AE	Adverse Event/Adverse Experience
BCVA	Best Corrected Visual Acuity
BSCVA	Best Spectacle Corrected Visual Acuity
CFR	Code of Federal Regulations
CLUE	Contact Lens User Experience
COAS	Complete Ophthalmic Analysis System
COM	Clinical Operations Manager
CRA	Clinical Research Associate
CRF	Case Report Form
CRO	Contract Research Organization
CT	Center Thickness
CTP	Clinical Technical Procedure
D	Diopter
DMC	Data Monitoring Committee
eCRF	Electronic Case Report Form
EDC	Electronic Data Capture
ETDRS	Early Treatment Diabetic Retinopathy Study
FDA	Food and Drug Administration
GCP	Good Clinical Practice
HIPAA	Health Insurance Portability and Accountability Act
IB	Investigator's Brochure
ICF	Informed Consent Form
ICH	International Conference on Harmonization
IDE	Investigational Device Exemption
IEC	Independent Ethics Committee
IRB	Institutional Review Board
ISO	International Organization for Standardization
ITT	Intent-to-Treat
JJVC	Johnson & Johnson Vision Care, Inc.
LC	Limbus Center
logMAR	Logarithm of Minimal Angle of Resolution
MedDRA [®]	Medical Dictionary for Regulatory Activities
MOP	Manual of Procedures
NIH	National Institutes of Health
OD	Right Eye
OHRP	Office for Human Research Protections
OHSR	Office for Human Subjects Research
OS	Left Eye
OU	Both Eyes
PD	Protocol Deviation
PHI	Protected Health Information
PI	Principal Investigator
PIG	Patient Instruction Guide

PQC	Product Quality Complaint
PRO	Patient Reported Outcome
QA	Quality Assurance
QC	Quality Control
SAE	Serious Adverse Event/Serious Adverse Experience
SAP	Statistical Analysis Plan
SAS	Statistical Analysis System
SD	Standard Deviation
SOP	Standard Operating Procedure
UADE	Unanticipated Adverse Device Effect
USADE	Unanticipated Serious Adverse Device Effect
VA	Visual Acuity
UV	Ultraviolet
HEV	High energy visible
PG	Propylene glycol
IPA	Isopropyl alcohol

1. INTRODUCTION AND BACKGROUND

ACUVUE® OASYS® is manufactured with a UV-blocker that blocks at least 99% of UV-B radiation and at least 90% of UV-A radiation (i.e., Class 1 UV-blocking). The new UV-blocker in the Test lens extends these radiation-blocking capabilities.

1.1. Name and Descriptions of Investigational Products

Senofilcon-based contact lens containing a new-UV blocker.

1.2. Intended Use of Investigational Products

The intended use of the investigative product in this study is for correcting myopia and providing visual benefits in lighting situations where UV-A and/or High Energy Visible (HEV) light is present in the environment. During the study, each test article will be worn bilaterally in a daily wear modality for at least 6 hours per day and 5 days per week for approximately 2 weeks each. The subject will wear either the Test or Control article twice and the other study article once.

1.3. Summary of Findings from Nonclinical Studies

All previous pre-clinical findings were deemed satisfactory prior to proceeding with clinical trials on humans.

1.4. Known Risks and Benefits to Human Subjects

and Informed Consent. The material safety testing/lens release criteria was determined based on the Risk Assessment.

2. STUDY OBJECTIVES, ENDPOINTS AND HYPOTHESES

2.1. Objectives

Primary Objective

The primary objective of this study is to demonstrate non-inferiority of the Test lens compared to the Control lens with respect to CLUE comfort, Slit Lamp Findings and Distance Monocular logMAR Visual Acuity. This study will also aim to show that the Fit Acceptance rate is at least 90% for subjects wearing the Test lens.

Secondary Objective

The secondary objective of this study is to demonstrate non-inferiority of the Test lens compare to the Control lens with respect to CLUE Overall quality of Vision and Handling.

Exploratory Objective

This study also aims to explore the performance of Indoor, Outdoor and Driving performance using individual questionnaire items.

2.2. Endpoints

Primary Endpoints

The primary endpoints are as follows:

Biomicroscopy

Biomicroscopy will be assessed for each subject eye at all study visits (scheduled and unscheduled). The percentage of Grade 3 or higher slit lamp findings will be analyzed and will include corneal infiltrates.

Distance Monocular Contact Lens Visual Acuity

Distance monocular contact lens visual performance (logMAR) is assessed for each subject eye at the 2-week follow-up evaluation.

Fit Acceptance Rate

Acceptable lens fit will be assessed at all scheduled visits for each subject eye. Fit acceptance rate will be based on the lens fit acceptance of eyes wearing the Test lens only. Fit rates of the control lens will also be collected, but are not a primary endpoint.

CLUE Overall Comfort

Overall comfort scores are assessed using the Contact Lens User Experience (CLUE) questionnaire at the two-week follow-up. CLUE is a validated patient-reported outcomes questionnaire to assess patient-experience attributes of soft, disposable contact lenses (comfort, vision, handling, and packaging) in a contact-lens wearing population in the US, ages 18-65. Scores follow a normal distribution with a population average score of 60 (SD 20), where higher scores indicate a more favorable/positive response. (2016)¹.

Secondary Endpoints

The Secondary endpoints are as follows:

CLUE Overall Quality of Vision and Handling

Overall Quality of vision and handling scores are assessed using the Contact Lens User Experience (CLUE) questionnaire at the 2-week follow-up. CLUE is a validated patient-reported outcomes questionnaire to assess patient-experience attributes of soft, disposable contact lenses (comfort, vision, handling, and packaging) in a contact-lens wearing population in the US, ages 18-65. Scores follow a normal distribution with a population average score of 60 (SD 20), where higher scores indicate a more favorable/positive response (2016)¹.

Other Observations

Lens Preferences

Lens preferences will be assessed by patient reported outcome (PRO) questions regarding lens preference at the 2-week follow-up of the second wearing period. Subjects will be asked to choose for each preference item one of the following responses: Strongly Prefer the first lens, Prefer the first lens, no preference, prefer the second lens, strongly prefer the second lens. Lens preference questions consist of:

[REDACTED]

Driving Performance

Driving performance will be assessed by two individual patient reported outcome (PRO) questions at the 2-week follow-up evaluation. The individual items are as follows:

[REDACTED]

Indoor Performance

Indoor performance will be assessed by three individual patient reported outcome (PRO) questions at the 2-week follow-up evaluation. The individual items are as follows:

[REDACTED]

Outdoor Performance

Outdoor performance will be assessed by four individual patient reported outcome (PRO) questions at the 2-week follow-up evaluation. The individual items are as follows:

[REDACTED]

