5. TEST ARTICLE ALLOCATION AND MASKING

5.1. Test Article Allocation

This is a multi-site, partially-subject masked (control lens only) and randomized study. The study lenses will be worn in a bilateral and random fashion using a 2 treatment by 3 period (2×3) crossover design.

Permuted block randomization will be used to minimize the potential for treatment imbalance. A block size of two (2) sequences will be utilized. A computer-generated randomization scheme will be used to randomly assign subjects to one of the two possible lens wear sequences (TEST/CONTROL/CONTROL or CONTROL/TEST/TEST). The random scheme will be generated using the PROC PLAN procedure from SAS Software Version 9.4 or higher (SAS Institute, Cary, NC).

The study site must follow the randomization scheme provided and complete enrollment according to the randomization list and not pre-select or assign subjects. The randomized assignment of subjects will be performed at the first visit prior to the first fitting. The following must have occurred prior to randomization:

- Informed consent has been obtained
- Subject meets all the inclusion / exclusion criteria
- Subject history and baseline information has been collected

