1.23	Subjective Lens Fit Assessment	
Subjective Assessment of the Lens Fit. If the fit is graded as unacceptable based on the criteria below, then the subject is discontinued from the study and will not be replaced.
 
 1. Limbal exposure in any gaze 2. Edge lift 3. Insufficient and/or excessive movement in all three movement categories
1.24	Continuance	
For the subject to continue in the study, they must meet all three of the following criteria:
 
 1. Snellen visual acuity is 20/30 or better OD and OS 2. The lens fit is acceptable OD and OS 3. Investigator approval. If the Investigator does not approve the dispensing of the first study lens, then the study is terminated for that subject.
1.25	Dispense	
The lenses will be dispensed for 6-8 days
 
 1. The subjects should wear their lenses similar to the inclusion criteria: ≥ 6 hours

Visit 1: Treatment 1 Lens Fitting		
Step	Procedure	Details
		
per day, ≥ 5 days per week.
 
 2. The lenses will be worn as daily wear only. 3. All subjects will be provided Opti-Free® PureMoist® to be used in a rub regime. 4. Preservative-free rewetting drops are permitted if needed. 5. A patient instruction booklet will be provided. 6. The lenses must be stored in the supplied case out of direct sunlight. 
Note 1: In the event a lens is lost or damaged, the subject will return to the investigator site for replacement (extra lenses cannot be given at the dispensing visit).
 
Note 2: The subject's habitual contact lenses cannot be worn at any time during the study.

VISIT 2

The follow-up will occur 6-8 days after the initial dispensing. The subjects must enter the visit wearing their study contact lenses.

Visit 2: Treatment 1 Follow-Up 1		
Step	Procedure	Details
2.1.	Adverse Events and Concomitant Medications Review	
Review the subject's concomitant medications and record any changes from the previous study visit.
 
Record any adverse events or medical history changes from the previous study visit.

2.2.	Wearing Time	Record the average wearing time and comfortable wearing time.
2.3.	Compliance	Confirm compliance with the prescribed wear schedule. Outdoor and total hours will be asked.
2.4.	Subject Reported Ocular Symptoms	Subjects will respond to a verbal open-ended symptoms questionnaire.

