The sample size calculation for distance monocular visual performance was performed assuming that there was no difference between the Test and Control lenses to achieve a minimum statistical power of 80%. Assuming a mean of 0 LogMAR, a standard deviation of 0.10 (based on historical ACUVUE® OASYS®) and a correlation between eye of 0.80, 2000 replicating trials were simulated for the repeated measurements from the multivariate normal distribution.

Acceptable Lens Fit

Acceptable lens fit is a binary response as y=1 if a subject eye has an acceptable fit and 0 otherwise. The common reference rate of 95% was selected for the sample size calculation, since this is considered to be a more conservative reference proportion. Assuming a correlation 0.80 between measurements within the same subject and period; and assuming a correlation of 0.50 between measurements within the same subject across periods. A total of 2000 replicating trials were simulated to estimate a sample size with a minimum statistical power of 80%.

Slit Lamp Findings

There was no Grade 3 or higher SLFs in any of the four historical studies. Therefore an incidence rate of 0.5% was chosen based on previous research literature^{3, 4}. Assuming a correlation 0.50 between measurements within the same subject and period; and assuming a correlation of 0.30 between measurements within the same subject across periods. A total of 2000 replicating trials were simulated to estimate a sample size with a minimum statistical power of 80%.

Table 7: Sample Size Estimates and Power Calculations for Primary Endpoints

Endpoint	Number per Subjects to Complete	Power
Distance Monocular Visual Acuity	40	>99%
SLFs Grade 3 or Higher	120	86%
Acceptable lens Fit	70	83%
CLUE Comfort	60	80%

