14.4. Level of Statistical Significance

The primary and secondary hypotheses will be tested with a type I error of 5% individually.

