For the β coefficients, independent non-informative priors $N(0, 1000)$ will be used. For the variance of random effect of σ_{site}^2 an independent non-informative conjugate prior, inverse-gamma(0.001, 0.001) will be used. For Σ , non-informative conjugate priors inverse-wishart(3,S) will be used where S is a 3X3 variance-covariance matrix of y_{ijkl} . Starting values for the mean and variance of CLUE scores will be 60 and 400 (since standard deviation of CLUE is normalized to be 20), respectively. The Metropolis sampler algorithm as implemented in the SAS/STAT MCMC procedure will be used to estimate the posterior distribution of the unknown parameters. Inferences will be made based on the 95% posterior credible intervals for relevant parameters.

Hypothesis Testing

The null and alternative hypotheses for CLUE comfort non-inferiority of the Test lens relative to the control lens are as follows:

$$H_o: \frac{\beta_1 + \beta_2 + \beta_3}{3} \leq -5$$

$$H_A: \frac{\beta_1 + \beta_2 + \beta_3}{3} > -5$$

Non-inferiority will be declared if the lower bound of the 2-sided 95% credible interval of the difference between the Test lens and the control lens is greater than -5, i.e., $P(\frac{\beta_1 + \beta_2 + \beta_3}{3} > -5) \geq 0.975$. Superiority will be declared if the lower bound of the 2-sided 95% credible interval of the difference between the Test and Control lens is greater than 0, i.e., $P(\frac{\beta_1 + \beta_2 + \beta_3}{3} > 0) \geq 0.975$. Superiority will only be tested if non-inferiority is established.

Lens Fit Acceptance

Lens fit acceptance will be analyzed using a Bayesian Logistic regression random-effects model to estimate the proportion of subjects eyes wearing the Test lens having acceptable lens fitting. The regression model will include period, sequence of lens wear and first order carryover effect. Site, subject nested within site and eye within subject within site will be included in the model as random effects.

Let $y_{ijklm}=1$ if an acceptable lens fit is observed for eyes wearing the Test lens only and $y_{ijklm}=0$ otherwise for the m^{th} subject, from the l^{th} site, for the i^{th} eye in the j^{th} period using the k^{th} sequence.

$$Y_{ijklm} \sim \text{Binary } (p_{ijklm})$$

$$p_{ijklm} = \frac{\exp(\text{Numerator})}{1 + \exp(\text{Numerator})}$$

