$$\text{Numerator} = \beta_0 + \beta_1 \text{Lens}_{i[j,k]} + \beta_3 \text{period}_{j1} + \beta_4 \text{period}_{j2} + \beta_5 \text{sequence}_k + \beta_6 \text{Carry1}_{i[j,k]} + \gamma_1 + \delta_{m(l)} + \alpha_{j(m(l))}$$

We assume the random subject eye effects are i.i.d as $\alpha_{j(m(l))} \sim N(0, \sigma_{\text{eye/subject/site}}^2)$ for eye nested within subject within clinical site, the random effect for subject are i.i.d as $\delta_{m(l)} \sim N(0, \sigma_{\text{subject/site}}^2)$ for subject nested within clinical site and the random clinical site effects are i.i.d as $\gamma_m \sim N(0, \sigma_{\text{site}}^2)$ for $i=1, 2$ (eye), $j=1, 2, 3$ (period) $k=1, 2$ (Sequence) $l=1, \dots, 5$ (Site) $m=1, \dots, n_l$ (subject/site).

For the β coefficients, independent non-informative priors $N(0, 10000)$ will be used. For the variance of random effects of $\sigma_{\text{eye/subject/site}}^2$, $\sigma_{\text{subject/site}}^2$ and σ_{site}^2 , independent non-informative conjugate priors inverse-gamma (0.001, 0.001) will be used. The Metropolis-Hastings algorithm as implemented in the SAS/STAT 14.1 PROC MCMC procedure will be used to estimate posterior distributions of the unknown parameters. Inferences will be made based on the posterior credible interval for the relevant parameters.

Hypothesis Testing

With respect to Acceptable lens fit the null and alternative hypothesis for superiority is as follows:

$$\begin{aligned} H_0 &= p \leq 0.90 \\ H_1 &= p > 0.90 \end{aligned}$$

Where, p represents the proportion of subject eyes that achieve acceptable fit for the Test lens.

Success for acceptable fit will be declared if the lower bound of the 2-sided 95% credible interval of the proportion is greater than 0.90; i.e. $P(P > 0.90) \geq .975$.

Primary safety analysis:

Slit Lamp Findings

Grade 3 or higher slit lamp findings will be analyzed using a Bayesian Logistic regression random-effects model to compare the Test and Control lenses. The regression model will include baseline slit lamp findings, lens type, period, sequence of lens wear and first order carryover effect. Site, subject nested within site and eye within subject within site will be included in the model as random effects.

Let $y_{ijklmn}=1$ if a Grade 3 or higher SLF is observed and $y_{ijklmn}=0$ otherwise for the n^{th} subject, from the m^{th} site, assigned to the i^{th} study lens for the j^{th} eye in the k^{th} period using the l^{th} sequence.

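### Discontinuing subjects at any unacceptable fit, combined with an analysis of Test-lens records only, biases the primary fit acceptance rate upward when fit failures correlate within subject

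*Combined protocol and SAP*

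**What the plan says.** Section 2.2 defines the endpoint: "Fit acceptance rate will be based on the lens fit acceptance of eyes wearing the Test lens only". Section 14.5 (Lens Fit Acceptance) sets the outcome to 1 "if an acceptable lens fit is observed for eyes wearing the Test lens only", and gives the decision rule: "Success for acceptable fit will be declared if the lower bound of the 2-sided 95% credible interval of the proportion is greater than 0.90".

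Section 5.1 randomises subjects to "TEST/CONTROL/CONTROL or CONTROL/TEST/TEST". Section 7.2 repeats one rule at every fit assessment, whichever lens is worn (steps 1.23, 2.8, 3.9, 3.22, 4.9, 4.22, 5.8): if the fit is unacceptable, "then the subject is discontinued from the study and will not be replaced". Dispensing also requires acceptable fit in both eyes.

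For the fit sample size, section 14.2 takes a correlation of 0.80 within subject and period, "assuming a correlation of 0.50 between measurements within the same subject across periods". It also says: "The common reference rate of 95% was selected for the sample size calculation".

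Section 8.1 limits the efficacy sets to dispensed subjects. Section 14.3 defines an ITT set of all randomised subjects. Section 14.5 does not say which set the fit analysis uses. Section 14.9 rules out imputation in the main analysis.

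**The concern.** A Control-first subject must pass Control fit in both eyes at Visits 1, 2 and 3 before a Test lens is placed. One who then fails on Test in Period 2 contributes nothing in Period 3. If the eyes that fail on one lens tend to fail on the other, the Control-first group is depleted of likely Test failures before it supplies any Test data. That group supplies two of every three planned Test eye-periods, or 4 of 7 scheduled Test assessments (steps 3.22, 4.9, 4.22 and 5.8, against 1.23, 2.8 and 3.9 in the Test-first group).

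The planned model cannot undo this. Test-only data have three cells: Test-first Period 1, and Control-first Periods 2 and 3. Period, sequence and carryover are confounded across those cells. The Lens term in the section 14.5 equation is constant, so that equation does not match the outcome definition above it. Subjects removed on Control have no row in the data.

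Fit acceptance is one of four primary endpoints, and section 2.3 requires every primary and secondary hypothesis to be met. No other hypothesis tests fit. A Test lens sitting exactly at the unacceptable 90% boundary could pass this test far more often than intended.

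**Working it through.** **The plan's own figure.** Table 7 gives 83% power with 70 subjects completing, for 95% against 90%. With 35 subjects per sequence, two eyes and correlations 0.80/0.50, a Test-first subject's sum of 2 results has variance pq(2 + 1.6) = 3.6pq. A Control-first subject's sum of 4 has pq(4 + 3.2 + 4) = 11.2pq. The total is 35 × 3.6 + 35 × 11.2 = 518pq over 210 results. With pq = 0.0475, SE = √(518 × 0.0475)/210 = 0.0236. Two-sided Wald power is Φ(0.05/0.0236 − 1.96) ≈ 56%; one-sided it is about 68%. Treating the correlations as latent gives 71% and 81%. The 83% is not reproduced. It is not called an error, because the test statistic and visit structure of the plan's simulation are not given. The exercise does show that the correlation scale is unstated and matters.

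**Nominal error.** Section 14.4 says "The primary and secondary hypotheses will be tested with a type I error of 5% individually". The fit rule requires posterior probability 0.975, which is 2.5% one-sided.

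**Direction of bias, closed form (same eye, binary scale).** Let f_T and f_C be the failure rates and ρ the correlation. Then

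P(Test fail | Control pass) = f_T − ρ√[f_T(1 − f_T) f_C/(1 − f_C)].

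- Equal rates: this reduces to (1 − ρ)f. With ρ = 0.50 and f = 0.10 it is 0.05, so acceptance appears as 95% when the truth is 90%.
- f_C = 0.05: 0.10 − 0.5√(0.09 × 0.05/0.95) = 0.066, so about 93.4%.
- f_C = 0.02: the largest attainable ρ is √[(0.02 × 0.90)/(0.10 × 0.98)] = 0.43, so a binary 0.50 cannot occur.
- ρ = 0: no bias.

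**Simulation.** There are 65 subjects per sequence, true Test acceptance 90%, and one fit result per eye-period. A subject is removed at the first period with any unacceptable eye. Success means that the lower limit of a cluster-robust 95% logit interval exceeds 0.90, as a stand-in for the planned Bayesian model. Binary-scale runs calibrate the correlations at 90% acceptance (latent values about 0.97 and 0.79). At Control 95% and 98% the binary cross-period correlation is then about 0.45 and 0.35.

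| False success on the fit test | Control 90% | Control 95% | Control 98% |
|---|---|---|---|
| Full rule, binary scale | 45% | 31% | 17% |
| Full rule, latent scale | 23% | 16% | 11% |
| Control gate alone, binary scale | 34% | 16% | 7% |
| Control gate alone, latent scale | 17% | 8% | 5% |
| No discontinuation rule | 2–3% | 2–3% | 2–3% |

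Repeat runs of these settings agree to within about three points. With the binary correlation held at 0.50 for Control 95%, the gate alone gives 19%. With a binary cross-period correlation of 0.30, the full rule gives 20%, 13% and 9%, and the gate alone 13%, 9% and 6%.

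Where the bias sits (full rule, binary scale, Control 90%): Test-first Period 1 90.1%, Control-first Period 2 95.5%, Control-first Period 3 97.1%, pooled 94.0%. Pooled rates at Control 95% and 98% are 93.1% and 92.4%.

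**Does a model repair it?** In 150 simulated trials at true 90%, a Test-only random-effects probit averaged 0.924, and the same type of model fitted to both lenses averaged 0.898.

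**Analysis set.** If Test-first subjects who fail fit at Visit 1 are also dropped as not dispensed, the pooled rate is 0.955 to 0.970 against a truth of 0.90 (Control 98% to 90%, correlation 0.42). This counts every Test-first Period 1 failure as a Visit 1 failure, so it is an upper figure.

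**The case against.** - **The target can be read as conditional.** The hypothesis in section 2.3 concerns subjects wearing the Test lens, which could mean those who reach it. But Test-first subjects are unscreened and Control-first subjects are screened on Control, so the pooled rate describes neither group. What stands is that the plan must state its target.
- **The lenses differ.** A reader might infer identical geometry, so that a Control failure is as good as a Test failure. Table 1 does not support this: base curve and diameter match, but center thickness does not. The bias needs only some correlation between failures, not identity.
- **The 0.50 is a planning value.** Section 14.2 gives it across periods, not explicitly across lenses, and states no scale. This stands, and it is why both scales and a correlation of 0.30 are shown.
- **The Control rate is unknown.** Section 14.2 calls 95% a conservative reference, and its historical studies used the same two lenses, so Control acceptance may exceed 95%. Control 90% is the least favourable case shown, although if the lenses fit alike, a Test rate at the 90% boundary implies Control near 90% too.
- **The planned Bayesian model was not itself simulated for false success.** This stands. The Test-only random-effects run shows a smaller bias (0.924 rather than 0.940), so the tabulated rates are indicative.

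**Conclusion.** The point holds in conditional form. Following the plan as written gives a Test fit rate that is biased upward whenever fit failures correlate within subject across periods. Under the full rule, false success at a true 90% runs from about 11% to 45% over the two correlation scales and Control acceptance of 90% to 98%, against 2.5% nominal. The Control gate alone accounts for about 5% to 34%; the rest comes from removing subjects after a Test failure. The bias from the Control gate vanishes at zero cross-period correlation and shrinks as Control acceptance nears 100%. These sizes rest on an assumed Control rate, an unstated correlation scale, one result per eye-period and a stand-in interval.

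A reader might infer more than this:

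- That all Test data are pre-screened. Test-first Period 1 is not screened by Control, though it stays unselected only if Visit 1 failures are kept.
- That 45% is the chance of a false overall success. It is the least favourable setting shown, for one endpoint, and every other primary and secondary hypothesis must also be met.

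**What to change.** - **Model (14.5).** Fit the model to both lenses' fit outcomes over all three periods. Control fit is already collected (2.2). The Lens term in the printed equation then becomes estimable, and the equation and the outcome definition are reconciled. Keep the period terms and the eye, subject and site random effects.
- **Target.** Test the marginal Test-lens acceptance probability over all randomised subjects against 0.90, and state how it is averaged over periods and random effects.
- **Population.** Name the ITT set of section 14.3 for this endpoint, so that Visit 1 fit failures on either lens count despite the dispensed-only limit in section 8.1.
- **Sensitivity check.** Report the TEST/CONTROL/CONTROL Period 1 Test rate, including Visit 1 failures. It does not depend on the joint model's assumption that observed fits and shared subject effects explain the missing Test results.
- **Wording.** Revise section 2.2 so that the analysis is not restricted to Test-lens records.

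The discontinuation rule need not change, and no new data are needed. The cost is revised wording in sections 2.2, 8.1 and 14.5, one model specification, a slightly wider interval (SD of the estimate about 0.027 against 0.024) and a less favourable expected fit rate.
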